5.3.4. Supplementary Analysis

[Table 3](#) shows the supplementary analyses that will be produced for the primary endpoint.

Table 3: Supplementary Analyses

Supplemental Analysis	Methodology	Population	Handling of Intercurrent Events
Randomized Set analysis	ANCOVA	Randomized Set	
 - Data collected on or after receipt of additional standard-of-care therapy (for the LN cohort only) will be imputed using the value collected at the time of renal flare or extrarenal SLE flare - Data collected on or after treatment discontinuation will be imputed using multiple imputation
mFAS analysis	ANCOVA	mFAS	
 - Data collected on or after receipt additional standard-of-care therapy (for the LN cohort only) will be imputed using the value collected at the time of renal flare or extrarenal SLE flare - Data collected on or after treatment discontinuation will be imputed using multiple imputation
PPS analysis	ANCOVA	PPS	
 - Data collected on or after receipt of additional standard-of-care therapy (for the LN cohort only) will be imputed using the value collected at the time of renal flare or extrarenal SLE flare - Data collected on or after treatment discontinuation will be imputed using multiple imputation
Treatment policy analysis	ANCOVA	FAS	
 - All observed data is used regardless of receipt of additional standard-of-care therapy (for the LN cohort only) or treatment discontinuation.

Abbreviations: ANCOVA = analysis of covariance; mFAS = Modified Full Analysis Set; FAS = Full Analysis Set; LN = lupus nephritis; PPS = Per-protocol Set; SLE = systemic lupus erythematosus

Further details of these supplementary analyses are below.

- Randomized Set analysis: The primary endpoint will be analyzed in the same manner as the primary analysis, except using the Randomized Set instead of the FAS. The Randomized Set will only be analyzed if the FAS population excludes more than 10% of the Randomized Set.
- mFAS analysis: The primary endpoint will be analyzed in the same manner as the primary analysis, except using the mFAS instead of the FAS. The mFAS will only be analyzed if this population excludes more than 10% of the FAS.
- PPS analysis: The primary endpoint will be analyzed in the same manner as the primary analysis, except using the PPS instead of the FAS.
- Treatment policy analysis: The primary endpoint will be analyzed in the same manner as the primary analysis, except all observed data will be included, regardless of receipt of additional standard-of-care therapy or treatment discontinuation.

5.4. Secondary Endpoint Analysis

The secondary efficacy analyses will be based on the FAS. These analyses will be descriptive in nature, and no adjustment for multiplicity will be performed.

The analyses for participants in the LN cohort and participants in the IgAN cohort will be conducted and reported separately. Participants in each disease-specific cohort will be analyzed as randomized, regardless of actual treatment received.

Summary statistics will be computed and displayed by treatment group and by visit, where applicable. Descriptive statistics for continuous variables will minimally include the number of participants, mean, SD, minimum, median, and maximum. For categorical variables, frequencies and percentages will be presented.

For the IgAN cohort, participants initially randomized to the placebo treatment group will receive ravulizumab in the Extension Period. Therefore, analysis of the secondary endpoints during the Extension Period (Week 26 through Week 50) will be summarized separately for each treatment group assigned during the Initial Evaluation Period (Baseline through Week 26).

During the Extension Period, baseline for the placebo treatment group will be redefined as the last measurement taken before the first dose of ravulizumab during the Extension Period (ie, the Week 26 measurement).

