9.4.1. Efficacy Analyses

9.4.1.1. Analyses of Primary Efficacy Endpoint

The primary analysis of the primary efficacy endpoint will be based on the Full Analysis Set (FAS).

For the LN cohort, proteinuria will be measured by UPCR in g/g derived from a single 24-hour urine collection at Screening and the mean of 2 separate 24-hour urine collections at Week 26.

For the IgAN cohort, proteinuria will be measured by absolute protein in g/day derived from the mean of 2 valid 24-hour urine collections.

To reduce skewness, the natural logarithm will be used to transform proteinuria values before analysis. An analysis of covariance (ANCOVA) will be used for the primary efficacy endpoint to compare reductions in proteinuria between the ravulizumab and placebo treatment groups. The ANCOVA model will include change from baseline in log-transformed proteinuria as the response variable and will adjust for baseline log proteinuria and the randomization stratification factor. The treatment effect will be evaluated using the least squares mean difference between treatment groups. The point estimate and two-sided 90% confidence interval (CI) for the mean difference of log-transformed proteinuria will be back-transformed (via exponentiation) to obtain the GMR and corresponding two-sided 90% CI. The values will then be expressed as percentage change in adjusted geometric mean of proteinuria at Week 26 relative to baseline.

For the LN cohort, data collected on or after receipt of additional standard of care therapy will be imputed using the proteinuria value from the 24-hour urine collection performed at the time of Renal Flare for the primary efficacy analysis. Additional sensitivity analyses will be performed to assess the impact of the missing data and assumptions.

For the IgAN cohort, participants initially randomized to the placebo group will receive ravulizumab in the Extension Period. Therefore, analysis of the secondary endpoints during the Extension Period will be summarized separately for each treatment group and baseline for the placebo group will be re-defined as the last measurement taken before the first dose of ravulizumab during the Extension Period (ie, the Week 26 measurement).

The primary efficacy endpoint analysis will also be performed on the Per Protocol Set.

Full details of these analyses will be provided in the SAP.

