5.1.2. Data Presentation for the Extension Period

Data summaries for the Extension Period will be presented by randomized treatment group and overall, if applicable. For the IgAN cohort, summaries will be presented by treatment sequence (ie, “Ravulizumab to Ravulizumab” and “Placebo to Ravulizumab”). In addition, baseline for the IgAN cohort will be defined as the last value prior to their initial exposure to ravulizumab.

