5.4.1. Proteinuria

The percentage change from baseline in proteinuria at Week 50 will be analyzed using a mixed-effect model for repeated measures (MMRM) using all available longitudinal data (either complete or partial). The model will include change from baseline in log-transformed proteinuria as the response variable and fixed, categorical effects of treatment group, randomization stratification factor, visit, and treatment group by visit interaction as well as a fixed, continuous effect of baseline log proteinuria as a covariate. An unstructured covariance matrix will be used to model the correlations among repeated measurements within each participant. If this analysis fails to converge, a first-order autoregressive covariance matrix will be used. The Kenward-Roger approximation will be used to estimate denominator degrees of freedom.

For the IgAN cohort, participants initially randomized to the placebo treatment group will switch to receive ravulizumab at Week 26. Therefore, percentage change from baseline in proteinuria at Week 50 will be summarized descriptively for each treatment group and for each visit from the MMRM analysis, and no formal treatment comparison will be made.

For the LN cohort, the treatment effect will be evaluated using a contrast for treatment group-by-visit term at Week 50. The point estimate and 2-sided 90% CI for the mean difference of log-transformed proteinuria will be back-transformed (via exponentiation) to obtain the GMR and corresponding 2-sided 90% CI. The values will then be expressed as percentage change in adjusted geometric mean of proteinuria at Week 50 relative to baseline.

This analysis will be performed 2 ways:

- Data collected on or after receipt of additional standard-of-care therapy (for the LN cohort only) will be imputed using the value collected at the time of renal flare, extrarenal SLE flare, suboptimal response, and data collected on or after treatment discontinuation will be assumed missing and handled in the MMRM as MAR.
- Data collected on or after receipt of additional standard-of-care therapy or treatment discontinuation will be assumed missing and handled in the MMRM as MAR.

In addition to the proteinuria analyses based on 24-hour urine collections, the percentage change from baseline in spot UPCR at each scheduled visit will be analyzed using an MMRM in a similar manner as above.

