5.4.2. Estimated Glomerular Filtration Rate

Kidney function evaluated by eGFR will be summarized at baseline and each postbaseline time point by treatment group using descriptive statistics for the observed value as well as the change from baseline and percentage change from baseline.

For participants in the LN cohort, baseline eGFR will be defined as the lowest measurement available prior to the first dose of study intervention. Screen failed values will not be considered.

For participants in the IgAN cohort, baseline eGFR will be defined as the mean of the Screening and Day 1 measurements.

For participants requiring dialysis for acute kidney injury, a value of 10 mL/min/1.73 m² will be imputed for while participants are on dialysis (ie, from the first day of dialysis through 5 days after the end of dialysis).

The longitudinal changes in eGFR will also be analyzed using the same MMRM method specified in Section 5.4.1.

This analysis will be performed 2 ways:

- Data collected on or after receipt of additional standard-of-care therapy (for the LN cohort only) will be imputed using the value collected at the time of renal flare, extrarenal SLE flare, suboptimal response, and data collected on or after treatment discontinuation will be assumed missing and handled in the MMRM as MAR.
- Data collected on or after receipt of additional standard-of-care therapy or treatment discontinuation will be assumed missing and handled in the MMRM as MAR.

The trajectory of eGFR over time will be visually presented by plotting the mean eGFR at each time point by treatment group.

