6.1.2. Definition of Baseline Values

For the Initial Evaluation Period, baseline is defined as the last available assessment value prior to the first dose of study intervention. For the Extension Period, baseline is defined as the last available assessment prior to the first dose of study intervention administered in the Extension Period.

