6.4.2. SAS Code for MMRM Analysis

The secondary endpoint of percentage change from baseline to Week 50 in proteinuria utilizes MMRM analysis. Other secondary endpoints assessing longitudinal changes will also utilize MMRM analysis. Sample code is provided below:

Step 1: Impute data on or after receipt of additional standard-of-care therapy (LN cohort only) using the value collected at the time of renal flare, extrarenal SLE flare, or suboptimal response, if applicable

Step 2: Analyze imputed dataset using MMRM analysis

```
proc mixed data=ADEF method=reml;
  class subjid trt01pn avisitn strat;
  model chg= trt01pn avisitn trt01pn*avisitn base strat /ddfm=kr solution;
  repeated avisitn/type=un subject=subjid;
  lsmeans trt01pn *avisitn/cl diff;
run;
```

where subjid is the patient identifier variable, trt01pn is the randomized treatment group, avisitn is the visit variable, base is the log(proteinuria) value at baseline, strat is the randomization stratification variable and chg is the change from baseline in log(proteinuria).

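### Read as written, the IgAN Week 50 MMRM mixes a Week 26 baseline (placebo arm) with a Day 1 baseline (ravulizumab arm); the SAP should fix one baseline for that model

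*SAP*

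**What the plan says.** Four places define the IgAN baseline for the Extension Period.

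- SAP 5.4, which opens the secondary endpoint section: "During the Extension Period, baseline for the placebo treatment group will be redefined as the last measurement taken before the first dose of ravulizumab". The ravulizumab arm is not mentioned, so its Day 1 baseline stands.
- Protocol 9.4.1.1 has the same rule, for secondary endpoints in the Extension Period: "baseline for the placebo group will be re-defined as the last measurement taken before the first dose of ravulizumab during the Extension Period".
- SAP 5.1.2 gives the same result in other words: "baseline for the IgAN cohort will be defined as the last value prior to their initial exposure to ravulizumab".
- SAP 6.1.2 differs: for the Extension Period, "baseline is defined as the last available assessment prior to the first dose of study intervention administered in the Extension Period". That is Week 26 for both arms.

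The model is in SAP 5.4.1. It is one MMRM on all available longitudinal data, with change in log proteinuria as response, one continuous baseline term, treatment-by-visit effects and one unstructured covariance. For IgAN, Week 50 "will be summarized descriptively for each treatment group and for each visit from the MMRM analysis", with no formal treatment comparison. Values after treatment discontinuation are set to missing and handled as missing at random. The code in 6.4.2 has one variable, described only thus: "base is the log(proteinuria) value at baseline". Spot UPCR is modelled in a similar way. For eGFR, 5.4.2 says "The longitudinal changes in eGFR will also be analyzed using the same MMRM method specified in Section" 5.4.1, but it also gives IgAN eGFR its own baseline, the mean of Screening and Day 1.

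**The concern.** Section 5.4 governs every secondary endpoint, and 5.4.1 does not exempt the MMRM from its re-baselining rule. Followed literally, the placebo arm contributes Y26 - Y0 at Week 26 and Y50 - Y26 at Week 50, while the ravulizumab arm contributes Y26 - Y0 and Y50 - Y0. The Week 26 value then enters the switch arm's two responses with opposite signs. One covariance matrix and one baseline slope cannot describe both arms.

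The shared covariance has a job to do: it is how the model uses Week 26 to make up for missing Week 50 values. At stake is the planned model-based estimate of how placebo participants respond after switching to ravulizumab, and its standard error. For spot UPCR the same issue would extend to every Extension visit.

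**Working it through.** **1. Inputs.** From SAP section 3: IgAN Week 26 to baseline ratios 0.85 (placebo) and 0.55 (ravulizumab), SD of log change 0.60, allocation 40:20, 10% dropout (36 and 18 evaluable), one-sided alpha 0.05. Assumptions, not in the documents: within-participant correlation rho; a Week 50 level of 0.55 of Day 1 in both arms; Week 50 more often missing when the Week 26 change is worse.

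**2. The plan's own figure.** With log(0.85/0.55) = 0.4353, SD 0.60 and 36 against 18, power is 0.807 (normal) or 0.798 (t). The stated 80% reproduces. It concerns Week 26 and does not depend on this point.

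**3. Correlation of the two changes, compound symmetry (variance s², correlation rho).**
- Each change has variance 2s²(1 - rho) = 0.60² = 0.36.
- Ravulizumab arm: Cov(Y26 - Y0, Y50 - Y0) = s²(1 - rho) = 0.18, correlation +0.50.
- Re-based placebo arm: Cov(Y26 - Y0, Y50 - Y26) = -s²(1 - rho) = -0.18, correlation -0.50.
- Pooled 2:1: (2 × 0.18 - 0.18)/3 = 0.06, and 0.06/0.36 = +0.17, true of neither arm.

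Under a first-order autoregressive structure with rho 0.5 to 0.85, the values are +0.61 to +0.68 against -0.25 to -0.07. The signs still differ.

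**4. Baseline slope at Week 50 on the Day 1 value, compound symmetry.** It is rho - 1 in the ravulizumab arm (-0.50 at rho 0.5, -0.15 at rho 0.85) and rho - rho = 0 in the re-based arm.

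**5. Effect on the switch-arm estimate.** True ratios are 0.55/0.85 = 0.647 from Week 26 and 0.550 from Day 1. Simulated 40:20 cohorts gave these mean estimates (rho 0.5 / rho 0.8):

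| Coding | None missing | Setting p = 0.10 | Setting p = 0.25 |
|---|---|---|---|
| Re-based, Day 1 covariate (true 0.647) | 0.645 / 0.645 | 0.682 / 0.691 | 0.723 / 0.727 |
| Re-based, Week 26 covariate (true 0.647) | 0.602 / 0.628 | 0.620 / 0.658 | 0.637 / 0.690 |
| Single Day 1 baseline (true 0.550) | 0.550 / 0.550 | 0.544 / 0.548 | 0.542 / 0.544 |

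Here p is the chance of a missing Week 50 value at the arm's average Week 26 change; the log-odds rise by 2 per unit of worsening in log change. Averaged over an SD of 0.60, p = 0.10 means about 15% missing and p = 0.25 about 30%. A separate simulation at SD 0.60 gave 0.66 with a Day 1 covariate and 12% missing, and 0.61 to 0.64 with a Week 26 covariate.

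**6. Why the Week 26 covariate shifts the estimate with nothing missing.** LS means are evaluated at the pooled covariate mean. Only 20 of 120 records carry the lower Week 26 baseline, lower by -log(0.85) = 0.1625, so the evaluation point lies 0.1625 × (1 - 20/120) = 0.135 above the switch arm's own. Multiplying by a slope of -0.5 or -0.2 gives -0.068 or -0.027, and exp(-0.435 - 0.068) = 0.605 and exp(-0.435 - 0.027) = 0.630. The simulated values are 0.602 and 0.628.

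**7. Against sampling error.** The SE is about 0.60/√18 = 0.14. Using simulated SDs, the log-scale bias is 0.053/0.156 = 0.34 to 0.066/0.152 = 0.43 of an SD at about 15% missing (Day 1 covariate), 0.116/0.172 = 0.67 at about 30%, and 0.072/0.120 = 0.60 at most with a Week 26 covariate and none missing.

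**The case against.** A reader might infer that the SAP definitely fits a two-baseline model. The documents do not go that far. No sentence feeds re-based values into the MMRM, and the 5.4 rule sits in a paragraph on how Extension results are summarized. A Day 1 baseline throughout is compatible with 5.4.1 and 6.4.2. Under 6.1.2 both arms would be re-based and the sign conflict between arms would vanish, although Week 26 and Week 50 records would still use different baselines under one slope. SAP 5.1 also says efficacy is summarized separately by period; models split that way would not share a covariance. The use of all longitudinal data and by-visit output from the model favour a single fit, but do not settle it. All this stands. It turns the point into what follows if the text is applied as written, and does not remove the need to say which reading is meant.

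A reader might also extend the point to eGFR. SAP 5.4.2 gives IgAN eGFR a specific Screening/Day 1 baseline in the section that specifies its MMRM, and a specific rule should prevail over the general one. Only confirmation is needed.

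Finally, the result is secondary and descriptive, with no between-arm test, and the bias depends on assumed correlation and missingness. That is correct and limits the weight of the point.

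**Conclusion.** The point holds as a conditional one. SAP 5.4, SAP 5.1.2 and protocol 9.4.1.1 state a re-baselining rule which, carried into the single model of 5.4.1, gives that model a covariance and a baseline slope wrong for both arms; 6.1.2 contradicts the rule. The opposite signs follow from algebra under compound symmetry and persist under the autoregressive alternative.

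The practical distortion is modest. It is negligible with complete data and a Day 1 covariate. It is about 1 to 4 percentage points with 12% to 15% missing and a Day 1 covariate, at most about 4.5 points with a Week 26 covariate and none missing, and about 8 points at roughly 30% missing. Every case is below one standard error. The ravulizumab arm also moves slightly, from 0.55 to about 0.53 at 15% missing with a Day 1 covariate. The larger issue for the report is definition: on the same assumptions, the switch arm's headline is a 45% reduction from Day 1 or a 35% reduction from Week 26, and the SAP does not say which the MMRM will give. A claim that the trial's conclusions are at risk is not supported, since the Week 26 primary ANCOVA is untouched.

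**What to change.** - In SAP 5.4 and 5.4.1, state that the IgAN 24-hour proteinuria and spot UPCR MMRMs use the pre-Day 1 baseline in both arms at every visit.
- Report the switch arm's on-ravulizumab effect as the within-arm LS-mean contrast, Week 50 minus Week 26, from that model.
- Restrict the Week 26 baseline to the separate descriptive Extension summaries.
- Align 5.1.2, 5.4 and 6.1.2, and define the baseline variable in 6.4.2 accordingly.
- Confirm in 5.4.2 that the IgAN eGFR MMRM keeps the Screening/Day 1 mean baseline.

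The cost is SAP wording and one ESTIMATE statement. There is a small downside: this narrows the re-baselining sentence in protocol 9.4.1.1, so it should be recorded in SAP 6.5. The headline switch-arm figure at Week 50 would then be relative to Day 1, with the Week 26-based figure supplied by the contrast.

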5.4.1. Proteinuria

The percentage change from baseline in proteinuria at Week 50 will be analyzed using a mixed-effect model for repeated measures (MMRM) using all available longitudinal data (either complete or partial). The model will include change from baseline in log-transformed proteinuria as the response variable and fixed, categorical effects of treatment group, randomization stratification factor, visit, and treatment group by visit interaction as well as a fixed, continuous effect of baseline log proteinuria as a covariate. An unstructured covariance matrix will be used to model the correlations among repeated measurements within each participant. If this analysis fails to converge, a first-order autoregressive covariance matrix will be used. The Kenward-Roger approximation will be used to estimate denominator degrees of freedom.

For the IgAN cohort, participants initially randomized to the placebo treatment group will switch to receive ravulizumab at Week 26. Therefore, percentage change from baseline in proteinuria at Week 50 will be summarized descriptively for each treatment group and for each visit from the MMRM analysis, and no formal treatment comparison will be made.

For the LN cohort, the treatment effect will be evaluated using a contrast for treatment group-by-visit term at Week 50. The point estimate and 2-sided 90% CI for the mean difference of log-transformed proteinuria will be back-transformed (via exponentiation) to obtain the GMR and corresponding 2-sided 90% CI. The values will then be expressed as percentage change in adjusted geometric mean of proteinuria at Week 50 relative to baseline.

This analysis will be performed 2 ways:

- Data collected on or after receipt of additional standard-of-care therapy (for the LN cohort only) will be imputed using the value collected at the time of renal flare, extrarenal SLE flare, suboptimal response, and data collected on or after treatment discontinuation will be assumed missing and handled in the MMRM as MAR.
- Data collected on or after receipt of additional standard-of-care therapy or treatment discontinuation will be assumed missing and handled in the MMRM as MAR.

In addition to the proteinuria analyses based on 24-hour urine collections, the percentage change from baseline in spot UPCR at each scheduled visit will be analyzed using an MMRM in a similar manner as above.

In addition to the MMRM analysis, observed values, change from baseline, and percent change from baseline in proteinuria will be summarized descriptively by treatment group at baseline and at each postbaseline time point separately by study phase.

The trajectory of proteinuria over time will be visually presented by plotting the mean proteinuria based on 24-hour urine collections at each time point by treatment group. This plot will be repeated for proteinuria based on spot UPCR.

The percentage of participants with > 30% reduction in proteinuria and > 50% reduction in proteinuria at Week 26 and Week 50 will be summarized by treatment group by calculating the point estimate and 2-sided 95% CI, based on exact confidence limits using the Clopper-Pearson method. Participants who receive additional standard-of-care therapy (for the LN cohort only) or discontinue treatment will be considered nonresponders from the point of treatment failure or treatment discontinuation onward.

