Days and Window	D -42 to -1	D1	D8 ± 2	D15 ± 3	D29 ± 3	D43 ± 5	D71 ± 5	D99 ± 5	D127 ± 5	D155 ± 5	D183 ± 5			
SLEDAI-2K		X										X	X	Perform as needed for evaluation of Extrarenal SLE Flare
Blood and urine samples for biomarkers	X	X		X			X		X			X	X	
Blood sample for anti-dsDNA and anti-C1q	X	B										X	X	
Blood and urine samples for RTCA	X	X		X			X		X			X		To be performed at selected sites only. See Section 8.9.3
Kidney biopsy ^k												X ^k		Send local pathology report and microscopy slides to the Central Pathology Laboratory (Section 8.1.5.3)
Administration of Study Intervention														
Randomization		X												
Allowed concomitant LN therapy	X	Continuous monitoring											Section 6.5.1	
Ravulizumab or placebo		X	X	X		X		X		-- ^l			Administer after all other required tests/procedures	

Note: All assessments should be performed prior to administration of study drug on dosing days, unless otherwise specified.

^a The Week 1 Visit is not required for participants enrolled after completion of the Dose Confirmation Analysis (Section 9.5.1).

^b Visit can be conducted at the discretion of the Investigator.

^c For participants who discontinue the study prior to the end of the Initial Evaluation Period, the ED Visit should be completed as soon as possible. In addition, a Follow-up Phone Call must be performed 8 weeks following the participant's last dose of study drug to collect information on concomitant medications, nonpharmacologic therapies and procedures, and AEs.

Table 1: Schedule of Activities During the Initial Evaluation Period: Screening to Week 26 Visit (LN Cohort)

^d Weight should be obtained at every visit and measured predose on dosing visits. The dose regimen is based on the last recorded study visit body weight. If the study drug is prepared the night before a visit, the weight from the most recent study visit should be used.

^e The 24-hr urine collection and spot urine samples must be obtained prior to or > 7 days after biopsy procedures.

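### The only MMRM fallback is AR(1) with one variance for all visits; for LN eGFR and spot UPCR it can misstate Week 50 uncertainty if the SD of change differs by visit

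*SAP*

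**What the plan says.** SAP 5.4.1 sets the covariance for the secondary proteinuria MMRM: "An unstructured covariance matrix will be used to model the correlations among repeated measurements within each participant". It gives one alternative, "If this analysis fails to converge, a first-order autoregressive covariance matrix will be used", and adds that "The Kenward-Roger approximation will be used to estimate denominator degrees of freedom". No heterogeneous or spatial structure and no robust standard error is named. The sample code in SAP 6.4.2 has only the unstructured form, "repeated avisitn/type=un subject=subjid".

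The model is reused. SAP 5.4.1 adds that "the percentage change from baseline in spot UPCR at each scheduled visit will be analyzed using an MMRM in a similar manner as above", and SAP 5.4.2 states: "The longitudinal changes in eGFR will also be analyzed using the same MMRM method specified in Section 5.4.1".

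The LN schedules (Protocol 1.3, Tables 1 and 3) place eGFR and spot urine at Weeks 1, 2, 4, 6, 10, 14, 18, 22, 26, 34, 42 and 50. Two of these visits are optional. For Week 1: "The Week 1 Visit is not required for participants enrolled after completion of the Dose Confirmation Analysis". For Week 6: "Visit can be conducted at the discretion of the Investigator". The 24-hour collections are scheduled only at Screening, Week 26 and Week 50 (Protocol 8.2.1).

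**The concern.** An unstructured matrix over 12 visits is demanding for about 60 participants, and more so when some visits are attended by a minority. If it fails, the plan leaves the analyst one choice.

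The SAP does not say homogeneous, but a plain first-order autoregressive matrix is ordinarily read as two parameters: one variance for all visits and one correlation per step between visits. A single pooled variance is wrong at any visit whose SD of change differs from the average. Kenward-Roger adjusts for small samples given the fitted structure; it does not correct a wrong one.

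Change in eGFR is called a key secondary endpoint (Protocol 4.2.2; SAP Table 1), and Week 50 is a named time point for it. At stake are the width and coverage of its Week 26 and Week 50 intervals, and those for spot UPCR.

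**Working it through.** The plan states no figure for MMRM convergence, covariance or coverage, so there is none to reproduce. Its only variability input is an SD of log change in proteinuria of 0.60 (SAP 3), with no SD or correlation by visit.

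**1. Parameter count.** Unstructured with K visits needs K(K+1)/2 parameters.
- LN eGFR and spot UPCR: 12 × 13 / 2 = 78.
- Without Weeks 1 and 6: 10 × 11 / 2 = 55.
- 24-hour proteinuria: 2 × 3 / 2 = 3.

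**2. How sparse Week 1 could be.** Dose confirmation uses the first 10 ravulizumab participants over both cohorts (SAP 5.8.1). At 2:1 that is about 10 × 3/2 = 15 randomized, plus any enrolled before the analysis is complete. The LN share is not given. With 13 or fewer LN participants at Week 1, that visit has no residual degrees of freedom (11 other visits + 2 arm means = 13).

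**3. Does unstructured fail?** Simulated REML fits, 8 data sets per setting:

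| Participants at Week 1 | 6 | 10 | 13 | 15 | 20 | 30 | All visits attended |
|---|---|---|---|---|---|---|---|
| Fits ending on a singular matrix | 7/8 | 7/8 | 8/8 | 7/8 | 6/8 | 1/8 | 0/8 |

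**4. Size if the SD grows (analytic).** Assume a participant's log series is a stationary process with correlation exp(−lag/d), d in weeks, plus noise of SD n. Its variance s² is set so that the SD of change at Week 26 is 0.60:

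2s²(1 − exp(−26/d)) + 2n² = 0.36.

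Take the 12-visit covariance conditional on baseline, find the AR(1) closest to it in Kullback-Leibler divergence, and compute

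ratio = AR(1) SD / true SD at the visit; coverage of a nominal 90% interval = 2Φ(1.645 × ratio) − 1.

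For d = 104 and n = 0.2, the AR(1) SD is 0.497 against a true Week 50 SD of 0.667. The ratio is 0.745 and coverage is 2Φ(1.226) − 1 = 0.78.

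| d (weeks) | n | Week 50 ratio | Coverage |
|---|---|---|---|
| 104 | 0.2 | 0.745 | 78% |
| 52 | 0.2 | 0.788 | 81% |
| 104 | 0.3 | 0.835 | 83% |
| 26 | 0.2 | 0.853 | 84% |
| 52 | 0.3 | 0.877 | 85% |
| 26 | 0.3 | 0.927 | 87% |

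Over the same grid the ratio is 0.88 to 0.95 at Week 26 (coverage 85% to 88%) and 1.12 to 1.57 at Week 2, where intervals are too wide. Heterogeneous AR(1) brings the Week 50 ratio to 0.92 to 1.00 (87% to 90%).

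**5. Does the direction hold in general?** AR(1) by REML with Kenward-Roger was simulated with 40:20 participants, Week 1 attended by 15, Week 6 by about half, and 10% dropout. There were 600 data sets per row (Monte Carlo error about 1.2 points). The patterns are assumed.

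| Pattern of SD of change | Mean SE / true SD of estimate, Week 50 | 90% CI coverage |
|---|---|---|
| Constant 0.60, equal correlations | 0.99 | 88.8% |
| Constant 0.60, correlation decaying in weeks | 1.05 | 93.2% |
| Rising 0.50 to 0.65 | 0.82 | 82.3% |
| Rising 0.40 to 0.70 | 0.73 | 77.2% |
| Diverging participant slopes | 0.83 | 82.8% |
| Change from baseline of a stationary series | 0.86 | 83.7% |
| Falling 0.70 to 0.50 | 1.25 | 95.7% |

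The first two rows keep the visit gaps of 1 to 8 weeks and show no shortfall beyond simulation error. The pooled variance, not the spacing, therefore drives the result. A variance specific to Week 50 (ANCOVA on observed Week 50 values) gave 88% to 93% in all seven rows. AR(1) with a sandwich standard error gave 86% to 91%.

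**The case against.** The strongest reply is that little rests on this fallback.
- The sentence chiefly concerns 24-hour proteinuria, the one endpoint with a spelled-out Week 50 LN contrast and 90% interval. With two visits and three parameters it should converge.
- Secondary analyses are descriptive and unadjusted (SAP 5.4). IgAN has no formal Week 50 proteinuria comparison and no Week 6 visit.
- Raw eGFR summaries by visit do not depend on the covariance.
- Failure of the unstructured fit is unproven. Week 1 attendance is not given, a visit that is not required may still take place, and the convergence check used only eight data sets per setting.

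All of this stands and limits the point to the LN eGFR and spot UPCR models. It does not remove it: descriptive results are still read through their intervals, and the fallback exists for the case in which convergence fails.

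Two stronger readings are tempting. A reader might infer that Week 50 intervals under the fallback are simply too narrow. The documents do not support that: they give no SD by visit, and a falling SD makes the intervals too wide. A reader might also blame the uneven visit gaps, but with constant SD coverage was 89% to 93%.

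**Conclusion.** The point holds conditionally. If Weeks 1 and 6 are sparsely attended, the unstructured MMRM for LN eGFR and spot UPCR may well fail, and the single AR(1) fallback then misstates uncertainty at any visit whose SD differs from the pooled value.

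If the SD of change grows over time, Week 50 standard errors are about 0.75 to 0.93 of the true value and a nominal 90% interval covers about 78% to 87%. Growth is plausible for change from baseline when within-person correlation fades with time, but it is assumed here.

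The size also rests on reading AR(1) as homogeneous and on the decay and noise ranges chosen. The 0.60 is a log-proteinuria figure. The ratio does not depend on units, so it carries over to eGFR only if the covariance has a similar shape, which the documents do not show. The primary ANCOVA is untouched. This is a recommended change, not an essential one.

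**What to change.** In SAP 5.4.1, and so by reference in 5.4.2, replace the AR(1) sentence with an ordered list: heterogeneous Toeplitz, then heterogeneous AR(1), using the first that converges. Both give each visit its own variance, so they guard against a rising or a falling SD. If a one-variance structure (AR(1), or spatial power in weeks) is kept as a last resort, pair it with a sandwich standard error. Add the fallback options to the code in SAP 6.4.2.

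Optionally, leave LN Weeks 1 and 6 out of these MMRMs, which cuts the unstructured parameters from 78 to 55. SAP 5.4.1 would then need matching edits where it calls for spot UPCR at every scheduled visit and for use of every available longitudinal observation.

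The cost is SAP wording and code options; no new data are needed. With 12 visits, the fallback would carry 12 + 11 = 23 parameters (heterogeneous Toeplitz) or 12 + 1 = 13 (heterogeneous AR(1)) instead of 2. Convergence of these two structures was not simulated, which is why the list is ordered. If Weeks 1 and 6 are dropped, they lose their model estimates but are still summarised descriptively.
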